2.4 Potential Risks & Benefits

2.4.1 Known Potential Risks

The side effect profile of hypertonic saline nebulization treatments remains low. There is some concern with treatments causing bronchospasm, but a retrospective cohort studied showed a 0.3% rate of occurrence of this side effect. The concern for bronchospasm seems to increase with the increase in concentration of hypertonic saline nebulization treatments, as formulations range from 3% to 7%. Other adverse events were reported in this study and showed a 1.0% rate of occurrence, and these events involved excessive coughing, which was transient. [6] Other side effects that have been reported such as hypernatremia, desaturation, bradycardia, vomiting and diarrhea were minor and spontaneously resolved. [5] There are no long-term risks associated with nebulized hypertonic saline and it is considered safe and inexpensive.

The side effect profile of chest percussion therapy, adverse effects of concern include excessive coughing and irritability. There were two case reports of rib fractures in children who received chest physiotherapy; however these were related to the more invasive forced expiratory techniques. Overall, the evidence lacked any statistically significant adverse outcomes following use of chest percussion therapy in children. [7] It can be concluded that chest percussion therapy is the least invasive of the chest physiotherapy techniques and the potential adverse effects of chest percussion therapy remain low.

There are no foreseeable physical, psychological, social, legal, or economic risks to participants by virtue of participation in this study. The value of information to be gained from this study may further guide clinicians on a more evidence-based approach to treatment of acute bronchiolitis in pediatric patients.

Because the study involves pediatrics, it is considered a study on a vulnerable population. There are no additional risks than those described previously.

Minimizing Risks

Because the study involves pediatrics, it is considered a study on a vulnerable population. There are no additional risks than those described previously.

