4.2.3 Exploratory Endpoints

There are no exploratory endpoints in this study.

5 Study Enrollment and Withdrawal**5.1 Inclusion Criteria**

In order to be eligible to participate in this study (experimental arm), an individual must meet all of the following criteria:

1. Age 0 to 24 months
2. Admitted to the general inpatient pediatrics unit
3. Has a diagnosis of acute bronchiolitis
4. Receiving supplemental oxygen support

Data collected for the control arm will be obtained via retrospective chart review for patients meeting the following inclusion criteria:

1. Age 0 to 24 months
2. Admitted to the general inpatient pediatrics unit

3. Has a diagnosis of acute bronchiolitis
4. Receiving supplemental oxygen support

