5.2 Exclusion Criteria

An individual who meets any of the following criteria will be excluded from participation in this study:

1. Admitted to the pediatric intensive care unit
2. Has an underlying pre-existing condition that may affect the respiratory system (includes bronchopulmonary dysplasia, reactive airways disease, asthma, restrictive lung diseases, other chronic lung diseases, etc.)
3. Has other comorbid conditions upon admission that may affect the respiratory system (includes pneumonia or other bacterial or fungal lung infections, acute exacerbation of reactive airways disease, acute exacerbation of asthma, pulmonary edema, pleural effusion, etc.)
4. Has an absolute contraindication to nebulized 3% hypertonic saline, for example, a history of an allergic or anaphylactic reaction
5. Is receiving other respiratory treatments such as bronchodilator treatments (i.e. albuterol or levalbuterol)
6. Is receiving other adjuvant therapy such as antibiotics, antivirals, glucocorticoids, corticosteroids, or diuretics

A potential study subject in the control arm via retrospective chart review who meets any of the following criteria will be excluded from this study:

1. Admitted to the pediatric intensive care unit
2. Has an underlying pre-existing condition that may affect the respiratory system (includes bronchopulmonary dysplasia, reactive airways disease, asthma, restrictive lung diseases, other chronic lung diseases, etc.)
3. Has other comorbid conditions upon admission that may affect the respiratory system (includes pneumonia or other bacterial or fungal lung infections, acute exacerbation of reactive airways disease, acute exacerbation of asthma, pulmonary edema, pleural effusion, etc.)
4. Has an absolute contraindication to nebulized 3% hypertonic saline, for example, a history of an allergic or anaphylactic reaction
5. Is receiving other respiratory treatments such as bronchodilator treatments (i.e. albuterol or levalbuterol)
6. Is receiving other adjuvant therapy such as antibiotics, antivirals, glucocorticoids, corticosteroids, or diuretics

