7.3.3 Intermediate Visits

7.3.3.1 Intermediate visits

Intermediate visits will vary from participant to participant depending on their length of stay during their inpatient at admission.

Intermediate visits (once per shift during duration of admission)

- Record adverse events as reported by participant or observed by investigator.
- Record vital signs, to include respiratory rate, heart rate, and oxygen saturation.
- Record current supplemental oxygen support settings.
- Administer the study agent or provide additional medication to the participant, in accordance with schedule – nebulized 3% hypertonic saline treatments combined with 3 minutes of chest percussion therapy every 6 hours while on supplemental oxygen support.
- Record participant's adherence to treatment program.
- Record subjective responses from providers and caretakers on participants' clinical response to treatment.

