8.3 Time Period and Frequency for Event Assessment and Follow-Up

The occurrence of an AE or SAE may come to the attention of study personnel during study visits and interviews of a study participant presenting for medical care, or upon review by a study monitor. All AEs including local and systemic reactions not meeting the criteria for SAEs will be captured on the appropriate RF. Information to be collected includes event description, time of onset, clinician's assessment of severity, relationship to study product (assessed only by those with the training and authority to make a diagnosis), and time of resolution/stabilization of the event. All AEs occurring while on study must be documented appropriately regardless of relationship. All AEs will be followed to adequate resolution.

Any medical condition that is present at the time that the participant is screened will be considered as baseline and not reported as an AE. However, if the study participant's condition deteriorates at any time during the study, it will be recorded as an AE. UPs will be recorded in the data collection system throughout the study.

Changes in the severity of an AE will be documented to allow an assessment of the duration of the event at each level of severity to be performed. AEs characterized as intermittent require documentation of onset and duration of each episode.

The PI will record all reportable events with start dates occurring any time after informed consent is obtained until 7 (for non-serious AEs) or 30 days (for SAEs) after the last day of study participation. At each study visit, the investigator will inquire about the occurrence of AE/SAEs since the last visit. Events will be followed for outcome information until resolution or stabilization.

All unresolved adverse events should be followed by the investigator until the events are resolved, the subject is lost to follow-up, or the adverse event is otherwise explained. At the last scheduled visit, the investigator should instruct each subject to report any subsequent event(s) that the subject, or the subject's personal physician, believes might reasonably be related to participation in this study. The investigator should notify the study sponsor of any death or adverse event occurring at any time after a subject has discontinued or terminated study participation that may reasonably be related to this study.

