10.4.4 Safety Analyses

Adverse events will be coded via Medical Dictionary for Regulatory Activities (MedDRA) and each adverse event will be counted once for occurrence. The severity, frequency and relationship of the adverse event to the study agent will be presented by the System Organ Class (SOC) and preferred term groupings. Information that will be reported about each adverse event will include start date and time of study agent, stop date and time of study agent, severity, relationship to event to study agent, and outcome. Adverse events will be ascertained and reported by the primary investigator. Adverse events leading to premature discontinuation from the study and serious adverse events requiring emergent treatment will be presented in a summarized listing.

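### Adverse events are planned for treated children only, with no abstraction from control charts, and an untimed intensive-care exclusion may remove controls who deteriorated

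*Combined protocol and SAP*

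**What the plan says.** **Who has adverse events recorded.** Section 8.3 opens the collection window at consent: "The PI will record all reportable events with start dates occurring any time after informed consent is obtained". Sections 7.3.3, 7.3.4 and 7.3.5 put the recording at study visits: "Record adverse events as reported by participant or observed by investigator". Section 8.7 directs the safety review at events that follow the study drug or the percussion cup. Section 10.4.4 presents the result by study-agent relationship, "The severity, frequency and relationship of the adverse event to the study agent will be presented by the System Organ Class", and lists among the reported fields "start date and time of study agent, stop date and time of study agent, severity, relationship to event to study agent, and outcome".

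**Where control data come from.** Section 5.1 states: "Data collected for the control arm will be obtained via retrospective chart review for patients meeting the following inclusion criteria". Sections 4.1 and 10.3 place these charts in the 12 months before the start date. Controls have no consent, no study visits and no study agent. No section names an adverse event to be read from their charts.

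**The exclusion.** Section 5.2 says that a potential subject in the "control arm via retrospective chart review who meets any of the following criteria will be excluded from this study". Item 1 is admission to intensive care, item 5 other respiratory treatments such as bronchodilators, and item 6 other adjuvant drugs. The list for the experimental arm has the same items in the same words. Neither list says when status is judged.

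**Deterioration and early stopping in treated children.** Under section 8.3, "if the study participant's condition deteriorates at any time during the study, it will be recorded as an AE". Section 5.7.1 lets the investigator end participation when an exclusion criterion newly develops. Section 5.7.2 says that no information on a participant who withdraws will be used. Section 10.4.5 drops children who leave early because of adverse events or for any other reason. Section 10.4.4 nevertheless plans a listing of events that led to discontinuation.

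**The concern.** Some of the events that the protocol treats as possible side effects can also be the illness itself. Section 2.4.1 says: "Other side effects that have been reported such as hypernatremia, desaturation, bradycardia, vomiting and diarrhea were minor". Section 2.1 describes bronchiolitis as progressing to respiratory distress and low oxygen saturation. Because any deterioration counts as an adverse event, the treated-arm table will mix disease course with any effect of treatment, and the plan holds no untreated count to set beside it.

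The intensive-care criterion adds to this. A chart review sees the whole admission, so a reviewer who applies item 1 to the finished chart removes a control who was transferred on day 2. A treated child with the same course has already been enrolled and the deterioration recorded. The two arms could then differ in transfers because of how children were selected.

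At stake is any comparative statement on the most serious disease-course events. Section 5.3 classes the study as greater than minimal risk in children aged 0 to 24 months, and section 8.7 sets no stopping rules. The efficacy analysis can run without this information.

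**Working it through.** **1. The plan's own figure.** Section 10.5 gives mean stay 6.5 days, SD 3.5 days, a 20% decrease, type I error 0.05 and power 0.80. The difference is 0.20 × 6.5 = 1.3 days. Two-sided, n per group = 2 × (1.960 + 0.842)² × 3.5² / 1.3² = 113.8, rounded up to 114, or 228 in total. The stated size reproduces (power 0.801). It was set for length of stay, and the documents give no size or rate for safety comparisons.

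**2. What the treated arm can show alone.** The chance of at least one event in 114 is 1 − (1 − p)^114.
- At the 0.3% bronchospasm rate cited in section 2.4.1: 29%.
- At the 1.0% rate cited there for other events: 68%.
- With 0 events, the upper limit of the exact two-sided 95% interval is 1 − 0.025^(1/114) = 3.2%.
- With an assumed 5 transfers, 5/114 = 4.4%, exact 95% interval 1.4% to 9.9%. Without a control rate, this is compatible with benefit, no effect or harm.

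**3. What disease course alone would produce.** The documents give no background rate for untreated children, so a range is assumed. At 5%, 114 × 0.05 = 5.7 treated children have the event with no harm from treatment. At 20%, 114 × 0.20 = 22.8. The plan has no control count to compare with these.

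**4. What the exclusion can do.** Assume that 5% of children in both arms are transferred after becoming eligible, so the true difference is zero.
- Item 1 applied to finished control charts, treated transfers counted: 0% of controls against an expected 5% of treated children, an apparent excess of 5 percentage points.
- Timing corrected for controls only, treated transfers dropped under sections 5.7.1 and 10.4.5: 5% against 0%, an apparent benefit of 5 points.
- Item 1 applied to later transfers in both arms: no transfer in either arm, so nothing to compare.
- Status judged at eligibility in both arms and all children kept: 5% against 5%.

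Only the last leaves the difference undistorted by the exclusion.

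**5. What a two-arm comparison could deliver with 114 per group.** With d the difference in rates, two-sided power = Φ[(d − 1.96 × SE₀) / SE₁], where SE₀ uses the pooled rate and SE₁ the separate rates. The half-width at equal rates is 1.96 × √(2p(1 − p)/114). For 5% against 10%: SE₀ = √(2 × 0.075 × 0.925/114) = 0.0349, SE₁ = √((0.0475 + 0.09)/114) = 0.0347, and power = Φ[(0.05 − 0.0684)/0.0347] = 0.30.

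| Assumed control rate | Treated rate detectable with 80% power | Power for a doubling | 95% half-width, percentage points |
|---|---|---|---|
| 2% | about 11% | 14% | 3.6 |
| 5% | about 16.5% | 30% | 5.7 |
| 10% | about 24% | 56% | 7.8 |
| 20% | about 37% | 91% | 10.4 |

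**The case against.** **No comparative safety objective is stated.** Sections 3 and 4.2 are about efficacy, and adverse event collection serves participant protection and reporting. That is fair, and it is why this point does not threaten the primary analysis. It does not make the treated-arm table interpretable for disease-course events.

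**Some comparison already exists.** Section 4.2.2 compares respiratory rate, heart rate and oximetry between groups, and time on oxygen is a primary endpoint. A reader might infer from the lack of control adverse events that the study can say nothing about desaturation or bradycardia. These planned comparisons rule that out. They are not event rates, however, and do not cover transfer, escalation of support or vomiting.

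**Causality is not left to one opinion.** A reader might infer that relatedness rests only on the unblinded investigator. Sections 8.4.1 and 8.4.2 send reported events to a departmental adverse drug event committee. Section 8.2.2 uses timing and response to withdrawal, and respiratory therapists are present at treatments (section 2.4.1). These help with acute reactions at dosing, such as bronchospasm. They do not supply a control rate for slower events.

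**The exclusion can be read differently.** A reader might infer that the control transfer rate is zero by construction. That holds only if item 1 covers later transfers. It can equally mean the unit of admission, paired with the inclusion criterion on the general unit, and it is worded identically for both arms. What stands is an ambiguity that should be settled.

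**114 per group is too few.** This is correct for testing, as the table shows, and historical, non-randomised controls limit the comparison further. It argues for estimates with intervals and against a formal test.

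**Conclusion.** The point holds in a limited form. The plan provides for no control-arm event data, so disease-course events have no control rate. Confinement to treated children is not stated outright. It follows from the consent-based window, the visit-based recording, the agent-linked fields and silence on control charts. The general statement in section 10.4.1 that descriptive statistics are calculated by group creates no control adverse event data.

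It would go too far to say that harm cannot be separated from disease course at all: vital signs are compared, and reactions close to dosing can be judged individually. The intensive-care criterion is a two-arm ambiguity whose effect depends on the reading adopted.

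The size rests on assumed background rates: about 6 to 23 of 114 treated children with an event at 5% to 20% and no harm, and an apparent difference of 5 percentage points in either direction if equal 5% transfer rates are handled unevenly. An amendment is worthwhile because the charts are already being opened. It would support a descriptive statement only.

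**What to change.** 1. **Section 5.2, both arms.** State that exclusions 1, 5 and 6 are judged on status when eligibility is met. Later transfers or newly started treatments are then counted as outcomes and do not remove the child from the data. Changing the control list alone would create the opposite bias. Leaving item 5 untimed would remove the very controls who started a bronchodilator.
2. **Sections 5.7.1, 5.7.2 and 10.4.5.** Reconcile these with each other and with the discontinuation listing in 10.4.4, so that treated children who stop early because of an adverse event or transfer stay in the safety comparison as far as consent permits. This concerns which data are analysed; it does not touch clinical decisions on treatment.
3. **Section 10.4.4.** Add a descriptive two-arm comparison of objective charted events: intensive-care transfer, escalation of oxygen support, desaturation and bradycardia on routine vital signs, vomiting, and bronchodilator started after eligibility. Use the same definitions and the same window, from eligibility to discharge, in both arms. Report risk differences with 95% confidence intervals and no formal test. Keep the investigator's adverse event table as a separate treated-arm listing.

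The cost is a few extra fields on the chart review of 114 controls and a short amendment. Softer events such as cough are likely to be under-recorded in charts and should stay out of the comparison. Only large differences will be detectable, and the report should say so.

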8.1.2 Definition of Serious Adverse Events (SAE)

Serious Adverse Event

Adverse events are classified as serious or non-serious. A **serious adverse event** is any AE that is:

- fatal
- life-threatening
- requires or prolongs hospital stay
- results in persistent or significant disability or incapacity
- a congenital anomaly or birth defect
- an important medical event

Important medical events are those that may not be immediately life threatening, but are clearly of major clinical significance. They may jeopardize the subject, and may require intervention to prevent one of the other serious outcomes noted above. For example, drug overdose or abuse, a seizure that did not result in in-patient hospitalization, or intensive treatment of bronchospasm in an emergency department would typically be considered serious.

All adverse events that do not meet any of the criteria for serious should be regarded as **non-serious adverse events**.

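### The serious-event listing in 10.4.4 is narrower than the SAE definition in 8.1.2, so some SAEs would not be identified as serious in any planned analysis output

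*Combined protocol and SAP*

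**What the plan says.** Section 10.4.4 plans three things for adverse events.

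- **A count and a table.** Events are coded in MedDRA, and "each adverse event will be counted once for occurrence". The table is described as follows: "The severity, frequency and relationship of the adverse event to the study agent will be presented by the System Organ Class (SOC) and preferred term". Nothing is filtered by seriousness, and seriousness is not among the displayed attributes.
- **Items reported per event.** "Information that will be reported about each adverse event will include start date and time of study agent, stop date and time of study agent", followed by severity, relationship and outcome.
- **A listing.** "Adverse events leading to premature discontinuation from the study and serious adverse events requiring emergent treatment will be presented in a summarized listing".

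Section 8.1.2 defines an SAE by six alternative criteria, one of which is that the event "requires or prolongs hospital stay". Section 8.3 governs collection: "Information to be collected includes event description, time of onset, clinician's assessment of severity", relationship, and the time at which the event resolved or stabilised. It adds that "AEs characterized as intermittent require documentation of onset and duration of each episode". It also sets the recording window, which runs to 7 days after the last day of participation for non-serious events and to 30 days for SAEs. Section 8.5 sends every SAE, related or not, to the sponsor on the SAE Form.

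**The concern.** The listing is the only place in 10.4.4 where seriousness appears, and its entry condition differs from the protocol's own definition. All participants are inpatients (5.1) and length of stay is a primary endpoint (4.2.1), so the hospital-stay criterion can be met without any emergency.

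The stake is the completeness of the safety report in a paediatric study that 5.3 classes as greater than minimal risk. Under 8.7 the principal investigator alone is responsible for safety review, without predefined stopping rules. Section 1 says that no biostatistician has yet been identified, so whoever joins will build the safety outputs from this text as it stands.

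**Working it through.** The plan gives no figure for this point, so there is none to reproduce. The check is a comparison of sections.

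**Step 1: is the listing condition a seriousness criterion?** The six criteria in 8.1.2 are death, threat to life, new or longer hospital stay, lasting disability, congenital anomaly, and important medical event. Emergent treatment is not one of them. The nearest is the last, whose examples include intensive emergency-department treatment of bronchospasm. That is one way of being serious, and it is not a condition placed on the other five.

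**Step 2: does another planned output show seriousness?**

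| Place | Content | Shows an unlisted SAE as serious? |
|---|---|---|
| 10.4.4 table | Severity, frequency and relationship by SOC and preferred term | No. Severity in 8.2.1 is mild, moderate or severe, a different scale from seriousness |
| 10.4.4 per-event items | Agent dates, severity, relationship, outcome | Seriousness is not named |
| 10.4.8 individual data | Primary and secondary outcomes | No. Adverse events are not covered |
| 8.5 SAE Form | Every SAE | Yes, but as expedited reporting and not as an analysis output |
| 8.7 annual IRB report | Safety review summary with accumulated events | Not specified, and not an analysis output |

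**Step 3: apply the rule to invented example records.**

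- *Bronchospasm that meets 8.1.2 and is treated emergently*: listed.
- *Vomiting that lengthens the admission, no emergent treatment, child stays in the study*: an SAE under 8.1.2. It is counted in the table and recorded on the SAE Form, but not listed and not marked serious in any planned output.
- *Readmission within 30 days after participation ends, no emergent treatment*: an SAE under 8.1.2 and inside the 8.3 window. Participation runs only to discharge (5.5), so the event cannot lead to discontinuation and is not listed.

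**Step 4: event times.** Section 10.4.4 names the start and stop of the study agent and does not name those of the event. Section 8.3 collects event onset and resolution. The data therefore exist, but the reporting list does not name them.

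**Step 5: the discontinuation half of the listing.** Section 10.4.4 promises to list events that led to discontinuation. Section 10.4.5 discounts from the study any participant who leaves early for an adverse event. Section 5.7.2 says that no information from before or after a withdrawal will be collected for use in the study, yet it also asks for safety follow-up of those who leave. Read literally, these provisions do not fit together.

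**The case against.** **Capture is complete and the events are still counted.** This stands. The table has no seriousness filter and the SAE Form takes every SAE. A reader might infer from the listing rule that serious events are undercounted, but the documents do not support that: the events are in the adverse-event counts and are only not labelled as serious there.

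**The restriction may rarely bite.** Section 10.4.7.1 says enrolment ceases on a caregiver's request or when an SAE occurs. If that is a rule for the individual child, an SAE would end participation and the event would enter the listing as a discontinuation. The wording is ambiguous between the child and the whole study, so this cannot be relied on. Even on the child-level reading, the readmission in Step 3 remains unlisted.

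**The dates are not wrong.** This also stands. A reader might infer that each event would be dated by the treatment course, with wrong onset and duration. But 10.4.4 only says what the reported information will include. It does not make agent dates stand for event dates, does not say whether they refer to the whole course or to one session, and does not exclude the times collected under 8.3. Clinicians grade relationship with onset already recorded. No proportion of misdated events can be derived from the text.

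**Conclusion.** The concern holds in a limited form. Following 10.4.4 as written gives an incomplete SAE display: an SAE without emergent treatment or discontinuation is not recognisable as serious in any planned analysis output.

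The size is qualitative. Adverse-event counts, SAE capture, expedited reporting and the efficacy analyses are unaffected, and the documents contain no SAE rate from which to project a number of unlisted events.

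The conclusion rests on two assumptions. The first is that no separate safety output is planned beyond those in Step 2; 10.1 says a formal SAP will be used, but the safety analyses given are those in 10.4.4. The second applies to the readmission example only: that the 30-day window in 8.3 is operated, although 5.5 says no follow-up period is required.

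The date wording is a secondary point about missing detail. The conflict between 10.4.4 and Sections 5.7.2 and 10.4.5 is separate. It could remove safety events altogether, so correcting the listing wording alone would not be enough.

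**What to change.** In 10.4.4:

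1. Drop the emergent-treatment condition, so that the listing covers all serious adverse events as defined in 8.1.2 together with events leading to discontinuation. Show emergent treatment as a column.
2. Add a count of serious events to the SOC and preferred-term table.
3. Name event onset and resolution date and time among the reported items, by episode where the event is intermittent. Keep the study agent dates as additional items.

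Reconcile 5.7.2, 10.4.5 and 10.4.7.1 with the discontinuation part of the listing, so that it is clear which safety data from children who leave early are reported and whether 10.4.7.1 refers to the child or to the study.

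Items 1 to 3 cost a few sentences. Seriousness is already captured through the SAE Form, event times are collected under 8.3, and emergent treatment must already be known to apply the present rule. The downside is a slightly longer listing and possibly a less favourable displayed SAE count.
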